#### **3.8.2. Analysis Windows**

Subject visits might not occur on protocol-specified days. Therefore, for the purpose of analysis, observations will be assigned to analysis windows.

In general, the baseline value will be the last nonmissing value on or prior to the first dose date of study drug.

HCV RNA, vital signs, and safety laboratory data collected up to the last dose date + 3 days are considered to be on-treatment data and HCV RNA, vital signs and safety laboratory data collected after the last dose date + 3 days are considered posttreatment data. The analysis windows for on-treatment HCV RNA, vital signs and safety laboratory data are provided in Table 3-1.

**Table 3-1. Analysis Windows for On-treatment HCV RNA, Vital Signs and Safety Laboratory Data**

Nominal Visit	Nominal Day	Lower Limit	Upper Limit
Baseline	1	(none)	1
Week 1	7	2	11
Week 2	14	12	18
Week 3	21	19	25
Week 4	28	26	32
Week 5	35	33	39
Week 6	42	40	49
Week 8	56	50	63
Week 10	70	64	77
Week 12	84	78	≥ 85

HCV RNA, vital sign, and safety laboratory data collected after the last dose date + 3 days will be assigned to the posttreatment follow-up (FU) visits. Visit windows will be calculated from the last dose date (ie, FU Day = collection date minus the last dose date) as shown in Table 3-2.

**Table 3-2. Analysis Windows for Posttreatment HCV RNA, Vital Signs and Safety Laboratory Data**

Nominal FU a Visit	HCV RNA			Vital Signs and Safety Laboratory Data b		
	Nominal FU Day	Lower Limit	Upper Limit	Nominal FU Day	Lower Limit	Upper Limit
FU-4	28	21	69	28	4	30
FU-12	84	70	146	NA	NA	NA
FU-24	168	147	210	NA	NA	NA

a FU-x visit = posttreatment Week-x follow-up visit.

b Vital signs and safety labs will only be summarized for the FU-4 visit (up to 30 days after last dose).

ECG data collected up to the last dose date + 3 days are considered to be on-treatment data. Qualitative assessments of whether the ECG is normal or abnormal will be assessed for on-treatment data based on the visit windows as shown in Table 3-3.

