## 7.5.2. Subject Stopping Rules

The Medical Monitor must be consulted prior to dose discontinuation of LDV/SOF FDC or SOF unless the investigator believes that immediate action is warranted to ensure the continued safety of the subject.

Due to a clinical or laboratory event, administration of all study drug(s) may be discontinued. There is no option for LDV/SOF FDC or SOF dose reduction. If LDV/SOF FDC or SOF is stopped due to toxicity, it must not be restarted. If SOF is discontinued then RBV must also be discontinued. If RBV is discontinued permanently, then SOF must also be discontinued. In these cases that study drug(s) are discontinued permanently, the subject must complete an ET visit. Posttreatment 4-Week, 12-Week and 24-Week visits must also be scheduled, 4, 12 and 24 weeks from the last dose of study drug.

Subjects who meet any of the following laboratory criteria must stop all study medication(s):

- Elevation of ALT and/or AST above the upper limit of normal and > 5x Day 1 or nadir, confirmed by immediate repeat testing
- Abnormal elevation of ALT > 3 x Day 1 *and* total bilirubin > 2 x ULN, confirmed by immediate repeat testing
- Elevation of ALT > 15 x ULN, confirmed by immediate repeat testing
- Any Grade 3 or greater rash associated with constitutional symptoms
- Any Grade 4 adverse event or laboratory abnormality assessed as related to LDV/SOF FDC or SOF

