#### 8.6. Safety Analysis

Safety will be evaluated by assessment of clinical laboratory tests, physical examinations, and vital signs measurements and AEs will be documented at various time points during the study.

All safety data collected, on or after the first dose of study drug administration up to 30 days after the last dose of study drug will be summarized by cohort and treatment group according to the study drug received.

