**Table 3-3. Analysis Windows for On-treatment ECG Data**

Nominal Visit	Nominal Day	Lower Limit	Upper Limit
Baseline	1	(none)	1
Week 1	7	2	45
Week 12	84	46	(none)

Note: ECGs are to be collected at screening, baseline, Week 1, and Week 12 or End of Treatment. For purposes of analysis, baseline value will be the last available value prior to the first dose of study drug and end of treatment value will be the last available value on or prior to the last dose date + 3 days.

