#### **7.5.           Electrocardiogram Results**

A shift table of the investigators' assessment of ECG results at each visit compared with baseline values will be presented by treatment group using the following categories: normal; abnormal, not clinically significant; abnormal, clinically significant; or missing. The number and percentage of subjects in each cross-classification group of the shift table will be presented. Subjects with a missing value at baseline or postbaseline will not be included in the denominator for percentage calculation. No inferential statistics will be provided.

A by-subject listing for ECG assessment results will be provided by subject ID number and visit in chronological order.

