#### **7.7.           Changes From Protocol-Specified Safety Analyses**

There are no deviations from the protocol-specified safety analyses.

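### The SAP has no ECG window after last dose + 3 days, so the result of a later early-termination ECG is left out of the only ECG summary, against the protocol's 30-day rule

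*SAP*

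**What the plan says.** **SAP, ECG rule.** The ECG paragraph of Section 3.8.2 (below Table 3-2) sets the limit: "ECG data collected up to the last dose date + 3 days are considered to be on-treatment data". It continues: "Qualitative assessments of whether the ECG is normal or abnormal will be assessed for on-treatment data based on the visit windows as shown in Table"; the reference is to Table 3-3. The note to Table 3-3 repeats the limit: "end of treatment value will be the last available value on or prior to the last dose date + 3 days".

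**SAP, other safety data.** Vital signs and laboratory data have the same 3-day on-treatment cut. Table 3-2 then gives them a separate follow-up Week 4 (FU-4) window covering days 4 to 30 after last dose, with the footnote "Vital signs and safety labs will only be summarized for the FU-4 visit (up to 30 days after last dose"). Table 3-2 has no ECG column.

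**SAP, ECG output.** Section 7.5 plans one summary, a shift table by visit against baseline in which missing is one of the categories, plus a by-subject listing. On percentages it says: "Subjects with a missing value at baseline or postbaseline will not be included in the denominator for percentage calculation". Section 7.7 states: "There are no deviations from the protocol-specified safety analyses".

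**Protocol.** Section 8.6 says that all safety data from first dose "up to 30 days after the last dose of study drug will be summarized by cohort and treatment group". Section 8.2.1.2 defines treatment-emergent data by the same 30 days, and Section 8.6.4 names the 12-lead ECG among the data to be listed and summarized. Appendix 2 schedules ECGs at Screening, Day 1, Week 12/EOT and ET, and at no posttreatment visit. On permanent discontinuation Section 7.5.2 says: "In these cases that study drug(s) are discontinued permanently, the subject must complete an ET visit".

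**The concern.** The protocol promises a 30-day summary period for safety data and includes ECGs in it. The SAP carries that promise through for vital signs and laboratory data but stops at day 3 for ECGs, without saying that this is a change.

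The ECGs left out are not a random subset. No ECG is scheduled after the end of treatment, so the gap falls mainly on subjects who stop early and attend the ET visit more than 3 days after their last dose. Some of them will have stopped because of toxicity, and adverse events leading to permanent discontinuation are the protocol's primary safety endpoint (Section 8.1.2). Without their results, the shift table describes mainly subjects who completed treatment.

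**Working it through.** The plan states no figure to reproduce here. The check applies the window rules to each possible day, then asks whether the gap can be reached and how many subjects it could involve.

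**1. Windows by days since last dose (d = 0 to 30, 31 possible days)**

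| Data | d = 0 to 3 (4 days) | d = 4 to 30 (27 days) |
|---|---|---|
| Vital signs, laboratory | on-treatment window, Table 3-1 | FU-4 window, Table 3-2 |
| ECG | on-treatment window, Table 3-3 | none |
| Protocol 8.6 | to be summarized | to be summarized |

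The count of unassigned ECG days is 30 - 4 + 1 = 27 of 31. For vital signs and laboratory data it is 0 of 31. Running the rules with last dose on Day 10, 30, 60 or 84 gives the same result each time.

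The open upper limit of the Week 12 row in Table 3-3 does not rescue a later ECG. The table covers on-treatment data only, and its note repeats the 3-day limit.

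**2. Can the gap be reached?** Yes. Protocol 7.5.2 requires the ET visit and Appendix 2 puts an ECG in it. Sections 3.4, 3.4.1, 6.5 and 7.5.2 set no interval between last dose and that visit; only the posttreatment Week 4, 12 and 24 visits are timed from last dose. A visit on day 4 or later therefore complies with the protocol.

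Before the ET visit the only scheduled ECGs are Screening and Day 1, so a late ET tracing is that subject's only scheduled post-baseline ECG. Table 3-3 and its note do mention a Week 1 ECG, but neither document's schedule contains one. If one were taken, the subject would keep that early value and still lose the ET result.

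**3. Completers.** The latest in-window Week 12 visit is Day 84 + 3 = Day 87. With last dose on Day 84, d = 87 - 84 = 3, so the ECG is included. A completer is affected only if dosing ended before Day 84 and the visit was late. For example, last dose on Day 83 and visit on Day 87 gives d = 4.

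**4. Number of subjects.** The documents give neither a discontinuation assumption nor ET timing. For scale only, assume:
- early discontinuation of 0-5%, which is 0 to 225 x 0.05 = 11.25, about 0 to 11 subjects;
- 25-75% of ET visits more than 3 days after last dose.

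At the upper discontinuation rate this gives 11.25 x 0.25 = 2.8 to 11.25 x 0.75 = 8.4 subjects. The overall range is about 0 to 8.

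The studies described in Protocol 1.2.2 point to the low end. All 140 subjects completed in the Japanese SOF+RBV study, and all 157 completed in the LDV/SOF group of the Japanese genotype 1 study. In the 12-week genotype 2 group, 25 of 26 completed, so 1/26 = 3.8% stopped early.

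**The case against.** The strongest defence is that almost nothing is lost. The shift table has a missing category, so the gap is visible, and the by-subject listing shows the actual tracing result. Protocol 7.1.3 requires abnormal ECGs associated with signs or symptoms to be recorded as adverse events when they meet the definition. SAP 7.1.5.1 counts events up to 30 days after stopping, and any event that led to stopping, as treatment-emergent. The 3-day cut also has a sensible origin, since on-treatment visits have a window of plus or minus 3 days. Finally, Protocol 8.6.4 leaves the type of ECG summary to what is appropriate.

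Most of this stands and limits the point to a minor one. It does not remove the conflict. The latitude in Protocol 8.6.4 concerns the kind of summary, not which collected ECGs count towards it. Three days is a reasonable definition of on-treatment, but it does not explain why nothing follows it for ECGs when a row follows it for the other safety data.

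A reader might infer four stronger things, which the documents do not support:
- *The subject vanishes from the table.* The missing category can still count the subject; what is lost is the result and the place in the percentage denominator.
- *The Day 1 ECG becomes the end-of-treatment value and shows no change.* The Table 3-3 note does not exclude this in words. However, Day 1 falls only in the Baseline window and post-baseline windows begin on Day 2, so a Day 1 tracing cannot fill a Week 1 or Week 12 row.
- *The ribavirin arm is affected more.* This is possible in principle, but the cited SOF+RBV study had no early stops among 140 subjects.
- *The on-treatment ECG period should simply be 30 days, as for laboratory data.* Laboratory data and vital signs keep the 3-day on-treatment cut and use a separate later row. Widening the ECG period would also misplace tracings: last dose on Day 10 with an ET ECG on Day 30 would fall in the Week 1 row (Days 2 to 45).

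**Conclusion.** The inconsistency is real and should be corrected, at low priority. As written, the SAP does not carry out Protocol 8.6 and 8.6.4 for ECGs taken 4 to 30 days after last dose, and the statement in SAP 7.7 is inaccurate on this point. That conclusion rests on the text alone.

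The practical effect is the absence of a few descriptive ECG results from one table, concentrated in early stoppers. The range of 0 to 8 subjects depends entirely on the assumed discontinuation and visit-timing rates. The efficacy analyses are unaffected, no inferential ECG analysis is planned, and the listing still shows every tracing.

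**What to change.** - Keep last dose + 3 days as the definition of on-treatment ECG data.
- In SAP 3.8.2, add a posttreatment/ET ECG window for days 4 to 30 after last dose, parallel to the FU-4 window for vital signs and laboratory data in Table 3-2. Give it its own row in the SAP 7.5 shift table. Unassigned ECG days then fall from 27 to 0.
- In the Table 3-3 note, define the end-of-treatment ECG as the last *post-baseline* value on or before last dose + 3 days. This closes the literal reading under which Day 1 could be returned.

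No new data are needed. The cost is a few lines of SAP text, a small programming change and one sparse row of off-drug ECGs, kept apart from the on-treatment rows. With this change the SAP 7.7 statement can stand on this point. If the 3-day limit is instead intended for all ECG summaries, SAP 7.7 should declare it as a change from the protocol.

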**Table 3-3. Analysis Windows for On-treatment ECG Data**

Nominal Visit	Nominal Day	Lower Limit	Upper Limit
Baseline	1	(none)	1
Week 1	7	2	45
Week 12	84	46	(none)

Note: ECGs are to be collected at screening, baseline, Week 1, and Week 12 or End of Treatment. For purposes of analysis, baseline value will be the last available value prior to the first dose of study drug and end of treatment value will be the last available value on or prior to the last dose date + 3 days.

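### SAP Table 3-3 gives the ECG analysis a Week 1 visit that neither study schedule contains, so early-termination ECGs can be tabulated as Week 1 results.

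*SAP*

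**What the plan says.** SAP 3.8.2 sets the ECG rules. On-treatment status comes first: "ECG data collected up to the last dose date + 3 days are considered to be on-treatment data". The normal or abnormal reading of each ECG then "will be assessed for on-treatment data based on the visit windows as shown in Table 3-3".

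Table 3-3 has three rows: Baseline (up to Day 1), Week 1 (nominal Day 7, Days 2 to 45) and Week 12 (nominal Day 84, Day 46 onward). Its note gives the collection times: "ECGs are to be collected at screening, baseline, Week 1, and Week 12 or End of Treatment". The note also states that the "end of treatment value will be the last available value on or prior to the last dose date + 3 days".

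SAP 7.5 turns these visits into output: "A shift table of the investigators' assessment of ECG results at each visit compared with baseline values will be presented by treatment group". Subjects without a baseline or postbaseline value are left out of the percentage denominator. A by-subject ECG listing is planned as well.

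The 12-lead ECG row in Protocol Appendix 2 is marked at Screening, Day 1, Week 12/EOT and ET, and is blank at Weeks 1, 2, 3, 4, 5, 6, 8 and 10. The ECG row in SAP Appendix 1 has the same four marks. The protocol synopsis and Protocol 6.7.5 mention on-treatment ECGs without naming Week 1. On permanent discontinuation for a clinical or laboratory event, Protocol 7.5.2 says: "In these cases that study drug(s) are discontinued permanently, the subject must complete an ET visit". SAP 7.7 declares no departure from the protocol's safety analyses.

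**The concern.** The SAP states an analysis visit, with its own window and its own row in a safety table, for an ECG that the trial does not schedule. The note conflicts with the protocol and with the SAP's own appendix.

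The conflict reaches the output. A programmer who follows the SAP will produce a Week 1 row with no scheduled data behind it. The entries that can reach it are unscheduled ECGs and ECGs from subjects who stopped treatment early. A reader of the clinical study report would take the row as a planned assessment one week into treatment. In fact it would hold end-of-treatment findings, or readings prompted by a clinical question, in a handful of subjects.

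**Working it through.** **Inputs.** Nominal days and limits from SAP Table 3-3; ECG rows from Protocol Appendix 2 and SAP Appendix 1; the rule of last dose + 3 days from SAP 3.8.2; the Week 1 laboratory window (Days 2 to 11) from SAP Table 3-1; the denominator rule from SAP 7.5.

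**1. Reproduce the window.** The midpoint of the two nominal days is (7 + 84)/2 = 45.5, so Week 1 ends on Day 45 and Week 12 starts on Day 46. This matches Table 3-3 exactly. The windows fit a schedule with two postbaseline ECG visits, at Week 1 and Week 12, so the Week 1 entry is built into the table and is not a stray word in the note.

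**2. Width.** Days 2 to 45 are 45 − 2 + 1 = 44 days. Days 2 to 84 are 84 − 2 + 1 = 83 days. The Week 1 ECG window therefore covers 44/83 = 53% of the postbaseline treatment period. The Week 1 window for laboratory data and vital signs is 11 − 2 + 1 = 10 days.

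**3. Scheduled ECGs that can fall in Days 2 to 45.** The Week 12/EOT visit (Day 84 ± 3, so Days 81 to 87) cannot. Screening and Day 1 are baseline. Only ET remains, plus unscheduled ECGs.

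**4. Where an ET ECG goes.** It is windowed only if its study day is at most the last-dose day + 3. It is then Week 1 if the day is 2 to 45 and Week 12 if the day is 46 or later.

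| Last dose | ET ECG | Label under Table 3-3 |
|---|---|---|
| Day 14 | Days 15 to 17 | Week 1 |
| Day 30 | Days 31 to 33 | Week 1 |
| Day 30 | Day 34 | none (not on-treatment) |
| Day 42 | Day 45 | Week 1 |
| Day 50 | Days 51 to 53 | Week 12 |

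The furthest displacement from the nominal day is 45 − 7 = 38 days. If a subject also has an earlier unscheduled ECG in the window, SAP 3.8.3 selects the record closest to Day 7, which may displace the ET record from the row.

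**5. Percentages.** Missing values leave the denominator. As an illustration only, suppose one subject in a Cohort 1 group has an ECG in Days 2 to 45 and it is abnormal. The Week 1 row reads 1/1 = 100% abnormal, in a group planned at 100 subjects (1/100 = 1%).

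**6. How many subjects.** The documents give no expected discontinuation rate, so the following is an assumption. Where Protocol 1.2.2 reports completion of 12 weeks, the counts are 140/140 (SOF+RBV, Japanese genotype 2), 157/157 (LDV/SOF, Japanese genotype 1) and 25/26 (LDV/SOF, genotype 2). Pooled, 1 of 323 did not complete. Applied to 225 subjects, 225 × 1/323 gives 0.7 early stoppers. With the genotype 2 LDV/SOF group alone, 225 × 1/26 gives 8.7. Only those who stop by about Day 45 and have an ET ECG within 3 days of the last dose would enter the Week 1 row.

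**The case against.** The best defence is that little follows from the discrepancy. SAP 7.5 has a missing category, excludes missing values from percentages, plans no inferential statistics for ECGs and lists every ECG by subject in chronological order. An almost empty row therefore biases no comparison, and each early stopper's result stays visible. The completion figures in Protocol 1.2.2 point to very few early stoppers. All of that stands, and it limits the size of the point. It does not make the row correct: the denominator rule is what lets one or two subjects produce a large percentage under a Week 1 label.

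Two stronger readings are tempting. A reader might infer that every ET ECG up to Day 45 is mislabelled. The documents do not support this, because an ECG taken more than 3 days after the last dose is not on-treatment and enters no window. A reader might also infer that these ECGs are lost from the end-of-treatment result. The Table 3-3 note defines an end-of-treatment value as the last one up to last dose + 3 days, so a windowed ET ECG is that subject's end-of-treatment value whatever its visit label. What remains open is whether that value is ever shown: Table 3-3 has no end-of-treatment row, and SAP 7.5 refers only to each visit.

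On the evidence, the column alignment of several other rows in SAP Appendix 1 is doubtful in the machine-read text. Protocol Appendix 2 therefore carries the weight; the four ECG marks agree in both.

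**Conclusion.** The point holds as an internal contradiction with a mislabelled safety output. SAP Table 3-3 and its note assume a Week 1 ECG that both schedules leave out. Followed literally, the Week 1 shift row contains only unscheduled ECGs, or ET ECGs from Days 2 to 45 that fall within last dose + 3 days. Its percentages rest on those few subjects.

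The consequence is small. It is confined to one descriptive table. The number affected is unknown and, on the completion rates assumed in the working, probably small. The by-subject listing keeps the individual results. SVR12 and the non-inferiority test do not depend on it. It is still worth correcting, because the rule is wrong as written and the correction is simple. The conclusion rests on the ECG rows being complete as printed, and the documents do not show whether a Week 1 ECG was ever intended.

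**What to change.** Reconcile Table 3-3 and its note with the ECG rows of Protocol Appendix 2 and SAP Appendix 1. The sponsor has to say which describes the trial.

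If the schedules stand, delete the Week 1 row and the words Week 1 from the note. State in SAP 7.5 that the shift table reports the end-of-treatment value already defined (last value up to last dose + 3 days, ET included), and keep unscheduled ECGs in the by-subject listing. If a Week 1 ECG was intended, both schedules must be brought into line with Table 3-3, and SAP 7.5 should still say whether the end-of-treatment value is shown.

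The first route costs an edit to one SAP table, its note and one sentence in SAP 7.5, with no new data. It has a downside: an earlier unscheduled ECG would appear only in the listing when a later one exists. An ET ECG taken more than 3 days after the last dose would also remain outside the table, as it does now.

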### **3.8.3. Selection of Data in the Event of Multiple Records in an Analysis Window**

Depending on the statistical analysis method, single values may be required for each analysis window. For example, change from baseline by visit usually requires a single value, whereas a time-to-event analysis would not require 1 value per analysis window.

If multiple valid nonmissing numeric observations exist in an analysis window, records will be chosen based on the following rules if a single value is needed:

- For baseline, the last available record on or prior to the date of the first dose of study drug will be selected. If there are multiple records with the same time or no time recorded on the same day, average (arithmetic mean) will be used for the baseline value. If multiple ECG measurements occur on the same day prior to first dose of any study drug, the average will be used as baseline value for continuous data, regardless of the timing of these multiple ECG measurements.
- For postbaseline visits:
  - The record closest to the nominal day for that visit will be selected except for HCV RNA posttreatment follow-up visits, for which the latest record in the analysis window will be selected.
  - If there are 2 records that are equidistant from the nominal day, the later record will be selected.
  - If there is more than 1 record on the selected day, the average will be taken, unless otherwise specified.

If multiple valid nonmissing categorical observations exist in a window, records will be selected as follows:

- For baseline, the last available record on or prior to the date of the first dose of study drug will be selected. If there are multiple records with the same time or no time recorded on the same day, the value with the lowest severity will be selected (eg, normal will be selected over abnormal). If multiple ECG measurements occur on the same day prior to the first dose of any study drug, the value with the lowest severity will be selected regardless of the timing of these multiple ECG measurements.
- For postbaseline visits, follow the same rules described above for postbaseline numeric observations, except that if there are multiple records on the same day, the most conservative value will be selected (eg, abnormal will be selected over normal).

